ZODIAC	Imperial College London	V.3 17 JAN 24
--------	-------------------------	---------------

potential patients as site staff will be part of their usual care teams. The patient information sheet will describe the study including any risks and potential benefits of enrolling. Written informed consent will be obtained from the patient prior to commencing any research procedures.

Patients will be given an adequate amount of time to consider their participation in the trial. If the patient agrees to participate in the trial they will be asked to sign the Informed Consent Form which will then be countersigned by the responsible clinician / researcher. The patient will retain one copy of the signed Consent Form. Another copy will be placed in the patient's medical records whilst the original will be retained in the research record for the patient at sites.

The right of the participant to refuse to participate without giving reasons must be respected. All participants are free to withdraw at any time from the protocol treatment without giving reasons and without prejudicing further treatment.

9.10 Participant Confidentiality

The investigator must ensure that the participant's confidentiality is maintained. On the eCRF or other documents submitted to the Sponsors, participants will be identified by a participant ID number only. Documents that are not submitted to the Sponsor (e.g., signed informed consent form) should be kept in a strictly confidential file by the investigator.

The investigator shall permit direct access to participants' records and source document for the purposes of monitoring, auditing, or inspection by the Sponsor, authorised representatives of the Sponsor, NHS, Regulatory Authorities and RECs.

9.11 Data Protection and Participant Confidentiality

The investigators and study site staff will comply with the requirements of the Data Protection Act 2018 concerning the collection, storage, processing and disclosure of personal information and will uphold the Act's core principles.

9.12 End of Trial

End of Trial will be when all study visits are complete, all data are captured on the database and the study database is declared clean and hard-locked.

9.13 Study Documentation and Data Storage

The investigator must retain essential documents until notified by the Sponsor, and for at least ten years after study completion. Participant files and other source data (including copies of protocols, CRFs, original reports of test results, correspondence, records of informed consent, and other documents pertaining to the conduct of the study) must be retained. Documents should be stored in such a way that they can be accessed/data retrieved at a later date. Consideration should be given to security and environmental risks.

No study document will be destroyed without prior written agreement between the Sponsor and the investigator. Should the investigator wish to assign the study records to another party or move them to another location, written agreement must be obtained from the Sponsor.

ZODIAC	Imperial College London	V.3 17 JAN 24
--------	-------------------------	---------------

10. DATA MANAGEMENT

10.1 Source Data

Source documents include original documents related to the trial - including participant medical history and participant medical treatment. Source documentation must be maintained to allow reliable verification and validation of the trial data. Source data for this trial will be defined in the Monitoring Plan.

10.2 Language

CRFs will be in English. Generic names for concomitant medications should be recorded in the CRF wherever possible. All written material to be used by participants must use vocabulary that is clearly understood, and be in the language appropriate for the study site in the UK, Spain and Italy.

10.3 Database

The trial data will be collected on an electronic case report form (eCRF). The principal means of data collection from participant visits will be Electronic Data Capture (EDC) via the internet using the OpenClinica database. Data is entered into the EDC system by trained site personnel. All data recorded in the eCRF will be signed off by the Investigator or his/her appropriate designee. All changes made following initial submission of data will have an electronic audit trail with a date. Specific instructions and further details will be outlined in the study specific eCRF manual.

10.4 Data Collection

Details of procedures for CRF/eCRF completion will be provided in a study manual.

10.5 Archiving

All trial documentation, including that held at participating sites and the trial coordinating centre, will be archived for a minimum of 10 years following the end of the study. All investigational sites will be responsible for archiving all trial documentation.

11. STUDY MANAGEMENT STRUCTURE

11.1 Trial Executive Committee

A Trial Executive Committee (TEC) will be convened including as a minimum an independent clinician, the Chief Investigator, National Leads and other international experts in the field. The role of this committee is to provide overall supervision of trial progress.

11.2 Early Discontinuation of the Study

In case of early discontinuation of the study, the Follow-up Visit assessments should be performed for each participant, as far as possible.

ZODIAC	Imperial College London	V.3 17 JAN 24
--------	-------------------------	---------------

11.3 Risk Assessment

A study-specific risk assessment will be performed prior to the start of the trial to assign a risk category of 'low', 'medium' or 'high' to the trial. Risk assessment will be carried out by the ICTU QA Manager in collaboration with the Study/ Operations Manager and the result will be used to guide the monitoring plan. The risk assessment will consider all aspects of the trial and will be updated as required during the course of the study.

11.4 Monitoring

The study will be monitored periodically by trial monitors to assess the progress of the study, verify adherence to the protocol, ICH GCP E6 guidelines and other national/international requirements and to review the completeness, accuracy and consistency of the data.

Monitoring procedures and requirements will be documented in a Monitoring Plan, in accordance with the risk assessment.

11.6 Quality Control and Quality Assurance

Quality Control will be performed according to ICTU internal procedures. The trial may be audited by a Quality Assurance representative of the Sponsor and/or ICTU. All necessary data and documents will be made available for inspection.

The study may be subject to inspection and audit by regulatory bodies to ensure adherence to GCP and the NHS Research Governance Framework for Health and Social Care (2nd Edition).

11.6 Peer review

The trial has been reviewed by senior members of ICTU and researchers at Imperial College London, as well as two independent peer reviewers.

11.7 Publication and Dissemination policy

Results will be presented at national and international scientific meetings to both cardiovascular and general physicians. All results will be published in high impact, general medical journals using open access policies and will be prepared in accordance with the internationally recognised standards for the publication of scientific results in peer-reviewed journals. We will communicate the results to the general public, we will also use appropriate media channels via Imperial College Public Relations team to disseminate results. All participating sites will be informed of the results and encouraged to disseminate findings via their own institutional social media platforms and patient and public engagement groups.

Information concerning the trial, patent applications, processes, scientific data or other pertinent information is confidential and remains the property of the Sponsor. The investigator may use this information for the purposes of the study only.

It is understood by the investigator that the Sponsor will use information developed in this clinical study and, therefore, may disclose it as required to other clinical investigators. In order to allow the use of the information derived from this clinical study, the investigator understands that he/she has an obligation to provide complete test results and all data developed during this study to the Sponsor.

ZODIAC	Imperial College London	V.3 17 JAN 24
--------	-------------------------	---------------

Verbal or written discussion of results prior to study completion and full reporting should only be undertaken with written consent from the Sponsor.

Therefore all information obtained as a result of the study will be regarded as CONFIDENTIAL, at least until appropriate analysis and review by the investigator(s) are completed.

The results may be published or presented by the investigator(s), but the Sponsor will be given the opportunity to review and comment on any such results for up to 1 month before any presentations or publications are produced.

A Clinical Study Report summarising the study results will be prepared and submitted to the REC within 90 days of the end of study.

ZODIAC	Imperial College London	V.3 17 JAN 24
--------	-------------------------	---------------

14.1 Sample GP Letter

Study Letter: Implementation of a Decision Support System and its effect on early optimisation of Lipid-Lowering Therapies in patients with Acute Coronary Syndrome: a cluster Randomised Controlled Trial

(insert date)

Dr. (insert GP name)

(insert GP address and contact details)

Dear Dr. (insert GP name),

Participant Name:

DOB:

Address:

RE: OptimiZation Of lipid lowering therapies using a Decision support system In patients with Acute Coronary syndrome (ZODIAC). REC Ref: 22/SS/0106/ IRAS Ref: 317589

I am writing to inform you that your patient named above has consented to participate in the above-named study, sponsored by Imperial College London.

Imperial College London has developed a Decision Support System (DSS) which is a web app available online intended for clinicians to estimate the clinical benefit and risk over time of Lipid Lowering Treatment regimens, whether single or combination therapies. Your patient has been invited to join as they are an adult (up to 80 years of age) with ACS who has recently been hospitalised (within 72 hours).

The aim of this study is to assess whether the availability of the DSS compared to routine care alone results in an increased initiation or intensification of combination LLTs over a 16-week period after an ACS event. This is a cluster randomised trial with a total of 48 hospital sites across the UK, Spain and Italy– 24 DSS sites and 24 non DSS sites. DSS sites will receive a standardised period of training; following the DSS use it is still up to the clinician to choose & prescribe a suitable therapy for the patient.

The participant will be followed up after the study Baseline Visit (i.e. post-ACS event) over a 4 month period as per routine care and study data will be captured accordingly. Aside from participant consent, there are no other participant study procedures.

This study has been approved by the relevant Ethics Committees and Regulatory authorities and will be conducted in accordance with Good Clinical Practice and appropriate regulatory requirements.

Please find enclosed a participant information sheet which provides more details about the study and what it involves for your patient. If you would like further information about the study, please do not hesitate to contact me.

[figure not shown]
Thank you in advance for your co-operation.

Kind Regards,

XXX

ZODIAC	Imperial College London	V.3 17 JAN 24
--------	-------------------------	---------------

Figure 2. Detailed Workflow for Estimation of the Impact of Lipid-Lowering Therapy Intensification via Monte-Carlo Simulation Based Approach

ZODIAC	Imperial College London	V.3 17 JAN 24
--------	-------------------------	---------------

Table 1. Illustration for Reporting Results of Simulation: Estimated Utilization of Lipid-Lowering Therapy

		A: Baseline (Observed SOC in the Database)	B: HIS Only at Index ACS	C1: HIS at Index ACS + Goal-Based Intensification*	C2: HIS + EZE at Index ACS	C4: HIS + EZE + PCSK9i at Index ACS
1	MIS Only			NA	NA	NA
2	HIS Only					
3	MIS + EZE			NA	NA	NA
4	HIS + EZE					
5	MIS + PCSK9i			NA	NA	NA
6	HIS + PCSK9i			NA	NA	NA
7	MIS + EZE + PCSK9i			NA	NA	NA
8	HIS + EZE + PCSK9i				NA	
9	EZE Only			NA	NA	NA
10	PCSK9i Only			NA	NA	NA
11	EZE + PCSK9i			NA	NA	NA
12	No LLT			NA	NA	NA

Note: For all scenarios (with the exception of baseline and HIS only at Index ACS) HIS only will be utilized as the comparator strategy. Thus, “NA” has been listed as all patients will be on a minimum of HIS only during follow-up. Further, the sequential application of treatments ensures that patients cannot be treated with ezetimibe without already being treated with HIS, or PCSK9i without already being treated with both HIS and ezetimibe.

* Ezetimibe added at 6 months and PCSK9i added at 12 months depending on LDL-C goal achievement (both LDL-C <1.4 mmol/L (55 mg/dL) and ≥50% reduction in LDL-C)

ZODIAC	Imperial College London	V.3 17 JAN 24
--------	-------------------------	---------------

Table 2. Illustration for Reporting Results of Simulation: Estimated LDL-C Goal Achievement

	A: Baseline (Observed SOC in the Database)	B: HIS Only at Index ACS	C1: HIS at Index ACS + Goal- Based Intensification*	C2: HIS + EZE at Index ACS	C3: HIS + EZE + PCSK9i at Index ACS
At 0-months					
LDL-C < 55 mg/dL					
55 ≤ LDL-C < 70 mg/dL					
70 ≤ LDL-C					
At 6-months					
LDL-C < 55 mg/dL					
55 ≤ LDL-C < 70 mg/dL					
70 ≤ LDL-C					
At 12-months					
LDL-C < 55 mg/dL					
55 ≤ LDL-C < 70 mg/dL					
70 ≤ LDL-C					

* Ezetimibe added at 6 months and PCSK9i added at 12 months depending on LDL-C goal achievement (both LDL-C <1.4 mmol/L (55 mg/dL) and ≥50% reduction in LDL-C)

ZODIAC	Imperial College London	V.3 17 JAN 24
--------	-------------------------	---------------

Table 3. Illustration for Reporting Results of Simulation: Estimated LDL-C Goal Achievement

	A: Baseline (Observed SOC in the Database)	B: HIS Only at Index ACS	C1: HIS at Index ACS + Goal-Based Intensification*	C2: HIS + EZE at Index ACS	C3: HIS + EZE + PCSK9i at Index ACS
At 0-months					
LDL-C < 55 mg/dL + LDL-C Reduction ≥ 50%					
LDL-C < 55 mg/dL + LDL-C Reduction < 50%					
LDL-C ≥ 55 mg/dL + LDL-C Reduction ≥ 50%					
LDL-C ≥ 55 mg/dL + LDL-C Reduction < 50%					
At 6-months					
LDL-C < 55 mg/dL + LDL-C Reduction ≥ 50%					
LDL-C < 55 mg/dL + LDL-C Reduction < 50%					
LDL-C ≥ 55 mg/dL + LDL-C Reduction ≥ 50%					
LDL-C ≥ 55 mg/dL + LDL-C Reduction < 50%					
At 12-months					
LDL-C < 55 mg/dL + LDL-C Reduction ≥ 50%					
LDL-C < 55 mg/dL + LDL-C Reduction < 50%					
LDL-C ≥ 55 mg/dL + LDL-C Reduction ≥ 50%					
LDL-C ≥ 55 mg/dL + LDL-C Reduction < 50%

2.1. Study Summary

The ZODIAC trial is an international, multicentre, cluster randomised, parallel arm trial. Its aim is to assess whether the availability and use of a Decision Support System (DSS) is more likely to result in implementation and achievement of European Atherosclerosis Society (EAS)/ European Society of Cardiology (ESC) lipid lowering goals, focusing on the early optimisation of lipid lowering therapy (LLT), in patients with Acute Coronary Syndromes (ACS).¹ ACS represent conditions compatible with acute myocardial ischemia and/or infarction. The study will be performed at approximately 48 investigational sites in the United Kingdom, Italy and Spain. DSS will be added to routine care and will be compared to routine care alone. Patients will be followed up for a maximum of 16 weeks.

2.2. Study Flowchart

[figure not shown]

Figure 1: Study flowchart

* In the event of under-recruitment of sites in Italy or Spain, up to 6 replacement sites may be recruited from UK.

3. Study Objectives

3.1. Primary Objectives

To compare implementation of a DSS (aligned to the 2019 EAS/ESC Guidelines¹) added to routine clinical care as compared with routine care without a DSS, to assess whether the addition of a DSS system to current practice increases the likelihood of intensification of LLT defined as escalation of monotherapy, initiation of combination therapy or escalation of combination therapy within a 16-week period.

3.2. Secondary Objectives

1. To compare the time to intensification of LLT in DSS versus routine care.
2. To compare the mean low-density lipoprotein cholesterol (LDL-C) and other key lipid variables by Week 16 in DSS versus routine care.
3. To compare the proportion of patients reaching target LDL-C level (<1.4 mmol/L (<55 mg/dL) by Week 16 in DSS versus routine care.
4. To compare the proportions of patients who receive different types of intensification of LLT: combination therapy by Week 16, escalated monotherapy by Week 16 and escalated combination therapy by Week 16 in DSS versus routine care.

3.3. Exploratory Objectives

For all patients, by treatment arm:

1. To determine the proportion of patients achieving target LDL-C level <1.8 mmol/L (<70 mg/dL) by Week 16
2. To determine the proportion of all cause and CV mortality by Week 16
3. To determine the proportion of patients experiencing myocardial infarction, stroke/TIA, admission for CV reasons and revascularization by week 16
4. To determine the proportion of patients prescribed combination therapies consisting of three oral LLT or 1 injectable therapy plus one or more oral LLT by Week 16
5. To determine whether the effect of the DSS on goal achievement (LDL-C < 1.4mmol/L by Week 16 or 55mg/dl) varies by institution setting, country, or subpopulations of interest (patients with a prior CV event in the 2 years prior to admission).

Imperial Clinical Trials Unit	ZODIAC STATISTICAL ANALYSIS PLAN – MAIN ANALYSIS	V1 17 th Jan 2024
-------------------------------	--	------------------------------

For LLT-naïve patients, by treatment arm:

6. To determine the proportion of patients achieving a decrease from baseline in LDL-C level of more than 50% by Week 16
7. To determine the percent change from baseline by Week 16 for:
 - LDL-C
 - non-high density lipoprotein cholesterol (non-HDL-C)
 - high-density lipoprotein cholesterol (HDL-C)
 - triglycerides
 - total cholesterol (TC)

In the DSS arm only:

8. To summarise LDL-C levels by Week 16 among patients who, on admission, are a) LLT naïve b) receiving monotherapy and c) receiving combination therapy
9. To carry out a qualitative evaluation of the DSS by the clinicians at DSS sites

In patients who are LLT-naïve on admission and who are prescribed combination therapy for at least 4 weeks by Week 16:

10. To determine the proportion of patients achieving target LDL-C level <1.4 mmol/L (<55 mg/dL) and a decrease of baseline in LDL-C level of at least 50% by Week 16 stratifying, where feasible, by different types of combination therapies e.g. oral combination therapies only, oral plus injectable combination therapy.

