4.1. Study Design

An international, multicentre, cluster randomised, parallel arm trial with a total of 48 sites randomised to Standard of Care (SoC) [24 sites] or DSS [24 sites] across 3 countries: the United Kingdom (UK), Spain and Italy. There will be 16 sites per country; 8 DSS sites; 8 SoC sites. In the event of under-recruitment of sites in Italy or Spain, up to 6 replacement sites may be recruited from UK. DSS sites will receive a standardised period of training prior to commencing patient recruitment. Patients will be followed up for a maximum of 16 weeks. As there are no defined study visits after the patient's baseline visit all outcomes will be assessed as close to 16 weeks as possible.

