5.5. Exploratory Variables

1. Proportion of patients achieving a decrease from baseline LDL-C level of more than 50% by Week 16 for LLT naïve patients
2. Percent change from baseline in LDL-C by Week 16 for LLT naïve patients
3. Percent change from baseline in non-HDL-C by Week 16 for LLT naïve patients
4. Percent change from baseline in HDL-C by Week 16 for LLT naïve patients
5. Percent change from baseline in triglycerides by Week 16 for LLT naïve patients
6. Percent change from baseline in total cholesterol by Week 16 for LLT naïve patients
7. Proportion of patients on combination therapy at Week 16 (for at least 4 weeks) achieving target LDL-C level <1.4 mmol/L (<55 mg/dL) and a decrease from baseline in LDL-C level of at least 50% by Week 16 for LLT naïve patients

Imperial Clinical Trials Unit	ZODIAC STATISTICAL ANALYSIS PLAN – MAIN ANALYSIS	V1 17 th Jan 2024
-------------------------------	--	------------------------------

8. Proportion of all patients achieving target LDL-C level <1.8 mmol/L (<70 mg/dL) by Week 16
9. Proportion of patients on combination therapies with three oral LLT or 1 injectable therapy plus one or more oral LLT
10. Proportion of patients with all-cause and CV mortality by Week 16
11. Proportion of patients with myocardial infarction, stroke/TIA, admission for CV reasons and revascularisations (CABG and/or angioplasty) by Week 16
12. Proportion of patients with goal achievement (LDL-C <1.4mmol/L or 55mg/dl by Week 16) in each trial arm stratified by institution setting (secondary/tertiary/mixed), country (UK/Spain/Italy) and by subpopulations defined by whether patients had experienced one or more CV events in the 2 years prior to admission.
13. LDL-C levels by 16 weeks among LLT-naïve (at ACS), monotherapy and combination therapy patients, within the DSS arm.
14. Quantitative evaluation as evaluated by the DSS Evaluation Questionnaire of the DSS by the clinicians at DSS sites

6. Estimands

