8.8. Subgroup Analysis (of Primary Outcome)

Subgroup analysis will follow the same analysis of the primary outcome with the addition of an interaction term between the treatment and the subgroup analysis variables. These will be summarised by forest plots.

The variables investigated in the subgroup analyses are (at patient level):

- gender (men vs women)
- age (below vs above or equal to median age)
- diabetes (yes vs no)
- LLT naïve (yes vs no)
- patients experiencing one or more CV event in the 2 years prior to admission

Below is an example model for an interaction between intervention and gender added.

$$\log(\pi_{ij}) = \beta_0 + \beta_1 ACSDSS_{ij} + \beta_2 COUNTRY1_{ij} + \beta_3 COUNTRY2_{ij} + \beta_4 Site\ type_{ij} + \beta_5 Site\ type_{ij} + \beta_6 Gender_{ij} + \beta_7 ACSDSS_{ij} * Gender + U_j$$

Where:

- π_{ij} : probability of combination therapy for the i^{th} patient in j^{th} site
- $ACSDSS_{ij}$: dummy variable for intervention ($ACSDSS_{ij} = 0$ or 1) for patient i in j^{th} site
- $COUNTRY1_{ij}, COUNTRY2_{ij}$: dummy variable for COUNTRY ($COUNTRY_{ij} = 0$ or 1) for patient i in j^{th} site
- $Site\ type1_{ij}, Site\ type2_{ij}$: dummy variable for Site Type ($Site\ type_{ij} = 0$ or 1) for patient i in j^{th} site type
- U_j : random effect for site $j \sim N(0, \sigma_u^2)$
- $Gender_{ij}$: dummy variable for gender of patient i in j^{th} site

Subgroup analyses at cluster level by site type is not planned as the number of sites is anticipated to be small for some strata.

Imperial Clinical Trials Unit	ZODIAC STATISTICAL ANALYSIS PLAN – MAIN ANALYSIS	V1 17 th Jan 2024
-------------------------------	--	------------------------------

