8.9. Exploratory Analysis

Proportions of those patients achieving the binary outcomes described in Section 5.5 will be described by frequencies and percentages by trial arm and for the overall population and by prespecified subgroups. No statistical significance testing will be performed for these analyses.

Mean (SD) and median (IQR) percentage change from baseline will be tabulated for each lipid measure.

The DSS Evaluation Questionnaire consists of 11 questions (see Table 43). Questions 1 to 10 are Likert responses scored from 1 (strongly disagree) to 5 (strongly agree) adapted from a previously published system usability scale (SUS).¹⁸ Question 11 is an additional question to capture overall user-friendliness of the DSS tool scored from six options from 'worst imaginable' to 'best imaginable'. Responses to the DSS Evaluation Questionnaire by the clinicians at DSS sites will be summarised descriptively using:

- mean (and range) score for each question (negative items (in italics in Table 43) will be reverse coded
- proportion of patients agreeing and disagreeing with each question (Questions 1 to 10)
- proportion who rated the DSS poor or worse in terms of overall user-friendliness (Question 11)
- proportion who deemed the DSS good or better in terms of overall user-friendliness (Question 11).

An overall usability score scaled from 0 to 100 will be computed from responses to Questions 1 to 10 only.¹⁸ A value of 1 is subtracted from the score of odd-numbered questions and the respondent's score is subtracted from 5 for even-numbered questions. These new values are summed and multiplied by 2.5 to give a score ranging from 0 to 100. Higher scores indicated greater usability.

Two additional open-ended questions (not included in the published SUS) have been included to capture suggestions for improvement of the DSS in terms of usability and examples of where the tool has been impactful in clinical practice. Responses to this question will be evaluated separately and are outside the scope of this SAP.

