Table 40: LDL-C goal achievement (LDL-C < 1.4mmol/L or 55mg/dl)by Week 16 by site type

Site type	Trial arm		
	DSS	Control	Overall
Secondary			
N (missing)			
n (%)			
Tertiary			
N (missing)			
n (%)			
Mixed			
N (missing)			
n (%)			

Table 41: LDL-C goal achievement (LDL-C < 1.4mmol/L or 55mg/dl)by Week 16 by country

Country	Trial arm		
	DSS	Control	Overall
UK			
N (missing)			
n (%)			
Italy			
N (missing)			
n (%)			
Spain			
N (missing)			
n (%)			

Table 42: LDL-C goal achievement (LDL-C < 1.4mmol/L or 55mg/dl) by Week 16 by CV event history

≥1 CV event in 2 years prior to admission	Trial arm		
	DSS	Control	Overall
Yes			
N (missing)			
n (%)			
No			
N (missing)			
Mean (SD)			

Table 43: Qualitative evaluation of DSS

Statement	Rating, mean (SD, range) ^a	Agreement with statement, n (%)	Disagreement with statement, n (%)
1. I think that I would like to use this tool frequently.			
2. I found the tool unnecessarily complex.			
3. I thought the tool was easy to use.			
4. I think that I would need the support of a technical person to be able to use this tool.			
5. I found the various functions in the tool were well integrated.			
6. I thought there was too much inconsistency in this tool.			
7. I imagine that most people would learn to use this tool very quickly.			
8. I found the tool very awkward to use.			
9. I felt very confident using the tool.			
10. I needed to learn a lot of things before I could get going with this tool.			
Statement	Rating, mean (SD, range) ^b	Poor or worse, n(%)	Good or better, n (%)
11. Overall, I would rate the user-friendliness of this tool as			

^a Score from 1 to 5 ^b Score from 1 to 6

Table 44: Qualitative evaluation of DSS – Standardised overall usability score (computed from Questions 1 to 10)

	Overall Usability Score (ranging from 0 to 100)
N (n missing)	
Mean (SD, range)	
Median (IQR)	

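### Exploratory objective 5 asks whether the DSS effect on the LDL-C goal varies by setting, country or prior CV event, but the planned output is raw percentages per arm, with no effect estimate or interval

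*SAP*

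**What the plan says.** - **Objective.** SAP 3.3, item 5: "To determine whether the effect of the DSS on goal achievement" (LDL-C below 1.4 mmol/L by Week 16) varies by institution setting, country or history of a CV event in the two years before admission. This is a question about effect modification. Items 1-4 of the same list ask only for proportions.
- **Variable.** SAP 5.5, item 12, turns it into "Proportion of patients with goal achievement (LDL-C <1.4mmol/L or 55mg/dl by Week 16) in each trial arm stratified by institution setting", country and CV-event history.
- **Analysis.** SAP 8.9: binary exploratory outcomes "will be described by frequencies and percentages by trial arm", overall and by prespecified subgroup, and "No statistical significance testing will be performed for these analyses".
- **Output.** SAP 12.8, Tables 40-42. Table 41, for example, is titled "LDL-C goal achievement (LDL-C < 1.4mmol/L or 55mg/dl)by Week 16 by country". Its columns are DSS, Control and Overall, and its rows are N (missing) and n (%).
- **Interaction models.** SAP 8.8: "Subgroup analysis will follow the same analysis of the primary outcome with the addition of an interaction term". The list holds patient-level variables, including prior CV event but not country. On setting it says "Subgroup analyses at cluster level by site type is not planned as the number of sites is anticipated to be small for some strata".
- **Model for this outcome.** SAP 8.5.3 specifies a log-binomial or modified Poisson model with site clustering for the LDL-C goal, without an interaction term.
- **Sites.** SAP 4.1: "There will be 16 sites per country; 8 DSS sites; 8 SoC sites".

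**The concern.** The objective asks whether an effect varies, and nothing in the plan estimates that variation or bounds it. A reader of Tables 40-42 can only subtract one arm's percentage from the other in each stratum and compare the results by eye. Those differences will never be exactly equal. For country and setting they rest on few sites per arm, so site-to-site variation alone can move them by several points. The tables give no means of judging how much of a visible difference is noise. What is at stake is the interpretation of an exploratory result. A country or setting might be described as one where the tool works better or worse when the data cannot support that. The primary and secondary analyses are not touched.

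**Working it through.** **1. Does any planned output address effect variation for this outcome?**

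| Place in SAP | LDL-C goal outcome? | Effect estimate with CI? | Interaction term? |
|---|---|---|---|
| 8.5.3 and Table 30 | yes | yes, overall only | no |
| 8.8 | no, primary outcome only | yes | yes, for patient-level variables including prior CV event; not country or site type |
| 8.9 and Tables 40-42 | yes | no | no |

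No row has all three.

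**2. Inputs for the size of the noise**
- From the SAP: 8 v 8 sites per country (4.1). The target of 792 patients over 24 sites per arm gives 792/24 = 33 per site (4.5). The ICC is 0.1 for planning; 4.5 takes about 0.1 for process variables and under 0.05 for the outcome variable, and reports 0.048 to 0.064 from hypertension guideline studies.
- Assumed, because the SAP gives none: goal rates (SoC/DSS) of 20/30, 30/30 and 30/40%; 16/5/3 sites per arm by site type; prior CV event in about 10% or 19% of patients.
- Yardstick: 10 points, borrowed from the planning difference of 0.05 to 0.15, which was set for another outcome.

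**3. The plan's own figure, as a check on the clustering formula.** (1.960 + 1.282)² × (0.05×0.95 + 0.15×0.85)/0.10² = 183.9 per arm. The design effect is 1 + 30×0.1 = 4, so 735.5 per arm, or 23.7 clusters of 31. Rounded up to 24, that is 744, as stated in 4.5.

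**4. Standard error of one country's raw arm difference**

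SE = √{[1 + (m−1)·ICC] × [p0(1−p0) + p1(1−p1)] / (8m)}

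At 30/40%, m = 33 and ICC 0.05: √(2.6 × 0.45/264) = 0.067. At ICC 0.1: √(4.2 × 0.45/264) = 0.085.

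**5. Chance of a spread of at least 10 points between the largest and smallest country difference when the true effect is the same everywhere.** At ICC 0.05 the threshold is 0.10/0.067 = 1.5 SEs. The range of three independent normal values exceeds that with probability about 0.54. Beta-binomial simulation (40,000 trials per setting) agrees. Ranges are over the three pairs of goal rates:

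| Split | ICC 0.02 | ICC 0.05 | ICC 0.1 |
|---|---|---|---|
| Country, ≥10 points | 30-38% | 46-54% | 62-68% |
| Country, ≥15 points | – | 19-26% | – |
| Site type (16/5/3), ≥10 points | – | 60-66% | 73-77% |

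With 4/12/8 sites per arm by type instead, 31 per site and goal rates from 20/30 to 40/50%, the site-type figures are 53-62% (ICC 0.05) and 67-74% (ICC 0.1).

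For prior CV event, under the same 31 per site and goal rates, the chance is about 6-25% across ICC 0 to 0.1. Both levels occur within every site, so the site effect largely cancels.

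**6. What the fix would show.** With 31 per site and 30/40%, one country's difference has a 95% half-width of 1.96 × √(2.5 × 0.45/248) = 13 points at ICC 0.05, and 1.96 × √(4 × 0.45/248) = 17 points at ICC 0.1. The difference in effect between two countries detectable with 80% power is 2.80 × √2 × SE, about 27 and 34 points.

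**The case against.** The strongest reply is that this is one of ten exploratory objectives, introduced as a summary by treatment arm, defined in 5.5 as stratified proportions, and analysed with an open statement that nothing will be tested. On that reading only the verb in 3.3 is wrong. Forgoing p-values is indeed legitimate, and the SAP sets no rule for declaring variation from the raw percentages. But an objective about whether an effect varies still needs an effect estimate and an interval, and disclaiming tests does not supply them.

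The reply is also right that the noise figures are conditional. A reader might infer that sizeable chance variation appears about half the time or more in all three splits. The documents do not support that. It needs an ICC of about 0.05-0.1 and the borrowed 10-point yardstick, and it is not true of prior CV event. Section 4.5 regards an ICC under 0.05 as reasonable for an outcome variable, and part of the reason for choosing 0.1 was clustering within country, which a within-country comparison removes.

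A reader might also see a contradiction between 8.8, which declines a site-type subgroup analysis, and Table 40. There is none: 8.8 concerns a model for the primary outcome, and a descriptive table for another outcome is compatible with it. The reason given in 8.8 does, however, apply equally to reading an effect difference out of Table 40.

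Finally, adding models will not let the trial settle the question, since only differences of roughly 27-34 points between countries would be detectable. That stands, and it is a reason to show the imprecision.

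**Conclusion.** The mismatch holds, and it does not depend on any ICC or goal rate: the plan poses a question of effect modification for LDL-C below 1.4 mmol/L and provides only raw percentages per arm. How misleading those percentages could be does depend on assumptions. For country, a chance spread of at least 10 points occurs in about 46-68% of trials at ICC 0.05-0.1, 30-38% at ICC 0.02, and 19-26% at ICC 0.05 if the yardstick is 15 points. Site type is noisier, at about 60-77% for ICC 0.05-0.1 with 16/5/3 sites per arm. Prior CV event is much less affected, at about 6-25%. Goal rates, site-type mix and prior-event prevalence are assumed, as is applying a 10-point yardstick to this outcome. If UK sites replace Italian or Spanish ones, as 4.1 allows, the smaller countries become noisier still. This is a minor, inexpensive improvement to an exploratory analysis and has no bearing on the trial's main conclusions.

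**What to change.** 1. **Country and prior CV event.** For LDL-C below 1.4 mmol/L, extend the 8.5.3 model with an arm-by-country term and, in a separate model, prior CV event and its interaction with arm. Keep the allowance for site clustering. Add to Tables 41 and 42 the stratum risk ratios and the ratios of risk ratios, each with a 95% CI, labelled exploratory. P-values are not needed, so the no-testing statement in 8.9 can stay.
2. **Site type.** Reword that part of objective 5 as a description of goal achievement by arm and site type. State that no inference about variation in effect will be drawn from Table 40, in line with the reasoning in 8.8.
3. **Table shell.** Correct the No row of Table 42, which asks for a mean and SD of a binary outcome.

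The cost is a few lines of SAP text and two further fits of a model already specified, with no new data. The drawback is that the intervals will be wide and only large between-country differences could be excluded. If the sponsor does not want to present such estimates, rewording the whole of objective 5 as descriptive would also remove the mismatch, but it would give up the question.
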